# 7.5. Withdrawal from the Use of Research Samples

The participant may withdraw consent for use of samples for research (refer to Long-Term Retention of Samples for Additional Future Research in Section 11.3). In such a case, samples will be destroyed after they are no longer needed for the clinical study. Details of the sample retention for research are presented in the ICF.

## 7.6. Lost to Follow-up

If a participant is lost to follow-up, every reasonable effort must be made by the study site personnel to contact the participant and determine the reason for discontinuation/withdrawal. The measures taken to follow-up must be documented. Refer to Section 7.3, Participant Discontinuation/Withdrawal from the Study.

#### 8. STUDY ASSESSMENTS AND PROCEDURES

For study assessments and procedures in the OLE period, see Section 10.8

#### 8.1. Overviewa

The SoA summarizes the frequency and timing of all assessments applicable to this study.

Repeat or unscheduled blood samples may be taken for safety reasons, additional PK samples or for technical issues with the samples.

Additional serum (by local laboratory) or urine pregnancy tests may be performed, as determined necessary by the investigator or required by local regulation, to establish the absence of pregnancy at any time during the participation in the study.

The total blood volume to be collected from each participant will be approximately 76 mL.

For each participant, the maximum amount of blood drawn from each participant in this study will not exceed 200 mL.

Volume of Blood to be Collected from Each Participant

			Approximate
	Volume per	No. of Samples	Total Volume
Type of Sample	Sample (mL)	per Participant	of Blood (mL) [a]
Hematology	2	5	10
Serum chemistry	2.5	5	12.5
Serology (HIV, hepatitis)	7.5	1	7.5
Serum β-HCG pregnancy test	1.5	1	1.5
Pharmacokinetic samples [b]	2	14	28
Biomarker Sample Collection	2	4	8
Pharmacogenomics	8	1	8
Approximate Total [c]			75.5

a. Calculated as number of samples multiplied by amount of blood per sample.

Note: An indwelling intravenous cannula may be used for blood sample collection.

#### Sample Collection and Handling

The actual dates and times of sample collection must be recorded on the laboratory requisition form. If blood samples are collected via an indwelling cannula, an appropriate amount (1 mL) of

\_

b. Includes the samples for JNJ-40411813 and metabolites, levetiracetam/ brivaracetam and

Repeat or unscheduled samples may be taken for safety reasons or technical issues with the samples.

<sup>a This section has been amended by Amendment INT-1

serosanguineous fluid slightly greater than the dead space volume of the lock will be removed from the cannula and discarded before each blood sample is taken. After blood sample collection, the cannula will be flushed and charged with a volume equal to the dead space volume of the lock. If a mandarin (obturator) is used, blood loss due to discard is not expected.

Refer to the SoA for the timing and frequency of all sample collections.

Instructions for the collection, handling, storage, and shipment of samples are found in the laboratory manual(s) that will be provided before the start of the study. The exact dates and times of blood sampling must be recorded in the CRF.

## **Study-Specific Materials**

The investigator will be provided with the following supplies:

- IB for JNJ-40411813.
- Pharmacy manual/study site investigational product manual or equivalent document e.g., Investigational Product Preparation Instructions.
- Laboratory manual.
- (Electronic) diary for participants and/or caregivers
- Electronic systems or paper documents for the completion of CCI and and C-SSRS.
- Only if available for this study: Electronic devices and manuals for remote seizure monitoring.
- Sample ICF.

## 8.2. Study procedures

#### 8.2.1. Screeninga

Participants will report to the clinical study center for the eligibility screening assessment just prior to the start of the 8-week baseline period. Participants will be asked to bring their current AEDs with them. Before any study specific procedures are conducted and following an explanation of the purpose and risks of the study, participants will sign an ICF and optionally the pharmacogenomics ICF. Recording of AEs/concomitant medication will start following consent and will continue until the final study visit. The screening assessments may be performed over multiple visits if deemed necessary for logistical reasons.

The eligibility screening examination will consist of the following:

- Complete medical history and demography
- Review of concomitant medication including AEDs
- Physical and neurological examination (including height and body weight)

<sup>a This section has been amended by Amendment INT-1

- Supine vital signs (systolic and diastolic blood pressure, oral or tympanic temperature)
- 12-lead ECG
- Clinical safety laboratory assessments under fasted conditions (at least 4 hours), when feasible (including serology, hematology, serum chemistry and urinalysis)
- Urine drug screen and alcohol breath test
- Serum pregnancy test for WOCBP
- The C-SSRS (baseline) is completed by the investigator or qualified delegate.
- Complete the diagnostic review form to initiate the adjudication process
- Record AEs
- Review inclusion/exclusion criteria

Exceptional and limited re-testing of abnormal screening values, including laboratory values, that lead to exclusion are allowed only once to reassess eligibility.

After the screening visit, the completed diagnostic review form of the participant will be sent to the epilepsy consortium for an adjudication process by independent experts. In this adjudication process the experts decide whether the participant meets eligibility criteria to participate in the study. If the adjudication process is not possible e.g., because of technical limitations of protected data transfer, the participant will not be a screen failure.

# 8.2.2. Baseline perioda

After screening, if they meet the in- and exclusion criteria for which data are available, participants can start the 8-week prospective pretreatment baseline period pending the results of the central laboratory and the adjudication process. However, when the results of these assessments indicate that the participant does not meet the in- and exclusion criteria, the participant will terminate the baseline period and will not be randomized to treatment.

When required for practical reasons, the baseline period may be up to 1 week longer or shorter than 8 weeks.

The participant and/or caregiver will be provided access to an (electronic) diary to record seizures. The e-diary will be an app downloaded on the smartphone owned by the participant. Only if the participant and/or caregiver do not own a smartphone, a smartphone programmed for the study will be provided.

During the baseline period, the participant will be contacted by phone by the investigator or study nurse to confirm correct use of the e-diary. This contact should take place at least 4 weeks after the start of the baseline period, but multiple contacts are allowed when required.

-

This section has been amended by Amendment INT-1

Participants must be compliant with the recording of information in the diary throughout the study. Seizures that will be entered during baseline and throughout the study include focal aware seizures with and without motor signs, focal impaired awareness seizures and focal to bilateral tonic-clonic seizures. Myoclonic, or other generalized seizures will not be entered.

#### 8.2.3. Treatment Perioda

Participants who complete the baseline period will be asked to come to the study center for Visit 2. Visit 2 should be planned in the morning hours, before noon (12.00 pm). Participants must report seizures in the e-diary from Day 1 through the following double-blind treatment period. When possible, participants have to come to the study center in fasting condition and will have a meal after the blood collection for clinical laboratory testing and biomarkers.

Participants who continue to meet entry criteria at the end of the baseline period must also meet the following criteria to be randomly assigned to treatment in the double-blind treatment period of the study:

- Have had between 3 and 100 seizures per 28 days within the first 4 weeks and also within the second 4 weeks of the baseline period.
- No seizure-free interval for more than 21 days

At Visit 2, before randomization and the first dose administration, all assessments (except post-dose PK blood collection) must have been completed.

The participant will visit the study center after 4, 8 and 12 weeks. After 2 and 6 weeks, the investigator will have a telephone call with the participant to discuss adverse events, use of the ediary and concomitant medication. Visits 2 (Day 1), 4 (4 weeks), and 6 (8 weeks) should be planned in the morning hours, before noon (12.00 pm). During the study visits, all assessments will be completed per the SoA. At each study visit, the participant should come to the study center in fasted condition (at least 4 hours) when possible and – during visits 2, 4, 6 and 7- will be dosed during or immediately after a meal at the study center after predose blood collections. Dosing should be witnessed by the study staff. At each study visit, participants should take their study intervention with them, and return used and partly used bottles.

During each study visit the following sequence of activities is preferred (not all activities at all visits. See the SoA for details):

- Collection of blood samples (clinical labs, pre-dose PK, biomarkers and pharmacogenomics)
- Pregnancy test
- Meal

• Scales (C-SSRS, CCI

Vital signs, 12-lead ECG

CONFIDENTIAL – FOIA Exemptions Apply in U.S.

<sup>a This section has been amended by Amendment INT-1

- Physical/neurological examination
- Dose of study intervention, levetiracetam or brivaracetam and other AEDs when applicable
- Review of e-diary, AEs and concomitant medication
- Post dose PK blood sample when applicable.

Participants and caregivers should continue to report seizures, new or extra concomitant medication and AEs during the full 12 weeks of the study when possible.

Participants are encouraged to complete at least the first 4 weeks of treatment when there are no safety concerns. Participants who have exceeded their pre-randomization monthly seizure count at Week 4, or within any 4-week interval after Week 4 ("4-week sliding window approach") up to Week 12, will have the option to discontinue the study drug for lack of efficacy and to perform the end of study/early withdrawal visit, or to continue double-blind treatment. Participants who have not exceeded the pre-randomization seizure count will continue the double-blind treatment period through Week 12.

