## DOSAGE AND ADMINISTRATION

JNJ-40411813 will be supplied for this study as 25-mg and 50-mg tablets. Placebo will be supplied as matching tablets.

The tablets will be taken **cc** from Day 1 to Day 85 (or day of Visit 7 when before Day 85). All study intervention, apart from the study intervention taken in the clinic during Visits 2, 4 and 6 will be taken at home and intake of the intervention should be confirmed in the e-diary.

Patients should be advised to call the site if they experience dizziness or somnolence in the first 2 weeks of the double-blind phase.

Study intervention should be taken in fed condition CCI

The tablets must be swallowed whole with water and not chewed, divided, dissolved, or crushed.

The CCI

during Visit 2 (Day 1) of the double-blind period when the participant is in the clinic in the morning. Dosing during the site visit will be witnessed by the study staff.

CCI

The participants will bring the study intervention and all other AEDs currently taken with them at each

On the day of Visit 4 (Week 4) and Visit 6 (Week 8), the CC will be taken in the study center during the study visit CC Dosing during the site visit will be witnessed by the study staff.

The actual dose and the composition of tablets to be taken will be determined for each cohort and stratum within a cohort.

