# 6.5. Concomitant Therapyb

All prestudy therapies administered up to 30 days before screening must be recorded at screening (and confirmed by treating physician).

During the 8-week prospective pretreatment baseline period and during the 12-week double-blind treatment period, participants will continue to take their prescribed AEDs (one of which must include levetiracetam or brivaracetam) without change in dosage(s); new concomitant AEDs should not be added. For the concomitant AEDs including levetiracetam or brivaracetam, all doses within the limits of current clinical practice will be allowed. Concomitant AEDs will not be provided by the study sponsor.

Two exceptions to this rule will be allowed:

<sup>a This section has been amended by Amendment INT-1

[figure not shown]
b This section has been amended by Amendment INT-1

- Based upon clinical judgment, a one-time dosage adjustment of concomitant AEDs is permitted to mitigate adverse events attributable to those AEDs. Collection of blood for plasma concentration of these AEDs is allowed, at the discretion of the investigator.
- One-time changes in AED dosages do not represent a change in the daily AED regimen. For example, if the participant took an extra dose of an AED on one day, this would not represent a change in the daily AED regimen.

Rescue medication may be used as needed (PRN). Each administration of rescue medication must be documented in the seizure e-diary. However, benzodiazepines or barbiturates received on a continuing basis at stable dosages for 1 month before screening should be considered as concomitant AEDs. Benzodiazepines or barbiturates used as sleep aid or to treat anxiety will be allowed but should be documented in the eCRF.

For levetiracetam or brivaracetam drug intake on the days of study visits, the same rule applies as for JNJ-40411813: On the day of Visits 2, 4, 6 and 7 CCI will be taken in the study center during the study visit and CCI. Dosing during the site visit will be witnessed by the study staff. CCI. Participants taking levetiracetam XR should preferably take their medication in the morning and take this medication in the clinic during Visits 2, 4, 6 and 7. If the participant takes levetiracetam XR in the evening, this should not be changed for the study.

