For study visits 2, 4, 6 and 7 participants are requested to record the time of last dosing of levetiracetam on the day before the study visit. Participants will also record the time that levetiracetam is taken at home prior to visit 7. An appointment-card will be provided for documentation.

Section 11.5 includes examples of disallowed CYP3A4 inhibitors (prohibited from 14 days or at least 5 times the drug's half-life, whichever is longer prior to study drug administration until the follow-up visit) and inducers (prohibited from at least 1 month prior to study drug administration until the follow-up visit).

Similarly, participants should avoid consumption of grapefruit, grapefruit juice and Seville oranges (including orange marmalade) and herbal products containing St. John's wort, ephedra, ginkgo, ginseng, or kava.

JNJ-40411813 itself is also an inhibitor of CYP3A4 and CCI or CYP3A4 metabolism and have a narrow therapeutic index with caution.

Examples of drug classes that include sensitive substrates to CYP3A4 and have a narrow therapeutic index include opioid analgesics, chemotherapy/oncologic agents, and immunosuppressive agents. Additional sensitive substrates that have a narrow therapeutic index include amiodarone, clindamycin, dihydroergotamine, dofetilide, ergotamine, and theophylline.

See Section 11.5 for an overview of drugs to be avoided.

If the administration of any concomitant therapy becomes necessary, it must be reported in the appropriate section of the eCRF.

The sponsor must be notified in advance (or as soon as possible thereafter) of any instances in which prohibited therapies are administered.

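### The protocol gives contradictory instructions on whether the Visit 7 doses are taken in the clinic or at home, so Week 12 blood samples can be predose at one site and postdose at another

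*Protocol*

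**What the plan says.** Text placing the Visit 7 doses in the clinic:

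- Protocol 8.2.3: participants "during visits 2, 4, 6 and 7- will be dosed during or immediately after a meal at the study center after predose blood collections", with staff as witnesses.
- Protocol 6.5, for levetiracetam/brivaracetam: "the same rule applies as for JNJ-40411813: On the day of Visits 2, 4, 6 and 7". Part of what follows is blacked out, but the study center is legible as the place of intake. Users of levetiracetam XR should preferably dose in the morning and "take this medication in the clinic during Visits 2, 4, 6 and 7".

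Text placing them at home, or leaving Visit 7 off the in-clinic list:

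- Protocol 1.1: "All study intervention, apart from the study intervention taken in the clinic during Visits 2, 4 and 6 will be taken at home". Section 6.1 repeats this.
- SoA (Section 1.2): the in-clinic intake rows for study drug and for background antiepileptic drugs are marked at Visits 2, 4 and 6 only.
- Protocol 6.4: participants record the times of study drug and levetiracetam/brivaracetam taken at home before Visit 7.
- Protocol 6.5, near the end: "For study visits 2, 4, 6 and 7 participants are requested to record the time of last dosing of levetiracetam on the day before" the visit, and in the next sentence "Participants will also record the time that levetiracetam is taken at home prior to visit 7".
- Table 3 (Section 6.6): the participant records the Visit 7 intake on the same day, ahead of the visit. Every cell of the during-visit line is marked not applicable.
- Morning scheduling in 8.2.3 omits Visit 7: "Visits 2 (Day 1), 4 (4 weeks), and 6 (8 weeks) should be planned in the morning hours". SoA footnote e does the same.

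Text on the Visit 7 blood samples:

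- SoA footnote i puts the clinical laboratory and biomarker samples before dosing. Footnote k draws the Visit 7 biomarker sample with the laboratory sample.
- Section 8.7 requires a fast of at least 4 hours for biomarkers and exempts only the Visit 2 postdose sample.
- Section 1.1: "Study intervention should be taken in fed condition".
- Table 4 (Section 8.5) times its samples from the in-clinic dose. It makes the Visit 7 pharmacokinetic (PK) sample postdose with no set time, and asks sites to combine it with other blood collection where they can.

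**The concern.** A site cannot comply with all of this, and the place of the dose decides the state of every Visit 7 blood sample. Sites that follow 8.2.3 produce fasting, predose laboratory and biomarker samples at Week 12. Sites that follow Table 3 produce postdose samples from participants who ate with the dose. Both kinds would then be reported under the same visit label.

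Three outputs are exposed:

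- the Week 12 safety laboratory summary;
- any Week 12 biomarker analysis;
- the descriptive Week 12 plasma concentrations, which are a secondary endpoint.

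Under Section 10.8.2.1, Visit 7 is also the baseline of the open-label extension for participants who enter it after a gap of 4 weeks or less. A mixed prandial state can therefore carry into the open-label laboratory changes from baseline that SAP 5.6.2.1 plans.

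**Working it through.** The plan states no figure to reproduce. The check sets current, legible sentences against each other and then counts the samples exposed.

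**Step 1. Can the sentences be reconciled?** No, in two pairs. Section 8.2.3 (dosed at the center, after predose bloods) opposes Table 3 (taken before the visit, with nothing to record during it). The main text of 6.5 (levetiracetam/brivaracetam in the study center on the day of Visit 7) opposes the end of 6.5 (levetiracetam at home before Visit 7). Section 6.4 adds a shorter in-clinic list, Visits 2 and 4, but it defers to 6.1 and says nothing further about where the Visit 7 dose is taken.

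**Step 2. What each reading breaks.**

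| Rule | Dose at home before Visit 7 | Dose in clinic at Visit 7 |
|---|---|---|
| SoA footnote i: labs and biomarkers predose | Broken | Met |
| 8.7: biomarker fast of at least 4 h | Broken unless the fed dose was at least 4 h earlier | Met if the participant arrives fasting |
| 8.2.3: dosing after predose bloods | Broken | Met |
| Table 3: Visit 7 recording | Met | During-visit cells marked not applicable |
| 1.1, 6.1 and SoA in-clinic lists | Met | Visit 7 absent |
| Table 4: postdose PK sample, combined when feasible | Can be met | Postdose sample needs a separate draw |

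In footnote i the allowance for feasibility attaches to fasting, not to the predose requirement.

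**Step 3. Share of samples per participant** (SoA and Table 4, checked against the blood-volume table in 8.1).

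- Clinical laboratory: screening and Visits 2, 4, 6, 7 = 5, matching 8.1. Visit 7 share 1/5 = 20%.
- Biomarkers: 2 at Visit 2, 1 at Visit 4, 1 at Visit 7 = 4, matching 8.1. Share 1/4 = 25%.
- JNJ-40411813 PK: 1 + 2 + 1 + 1 = 5. Share 1/5 = 20%.
- Levetiracetam/brivaracetam PK: 2 + 2 + 1 + 1 = 6. Share 1/6 = 17%. For evening levetiracetam XR users the Table 4 note gives 1 + 1 + 1 + 1 = 4, so 1/4 = 25%.
- The third Table 4 column has 1 + 1 + 1 + 0 = 3, and 5 + 6 + 3 = 14 PK samples, matching 8.1.

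**Step 4. Participants, as ceilings.** Randomized: 60 + 50 = 110 in two cohorts, or 60 + 50 + 50 = 160 in three. Treated with JNJ-40411813: 40 + 40 = 80, or 40 + 40 + 40 = 120. Visit 7 doubles as the early-withdrawal visit, so some of these participants take no dose that day. SoA footnote m also limits the early-withdrawal PK sample to withdrawals after Visit 6. No exit rate is given. If 0 to 40% leave at or before Visit 6 (an assumption), the PK count is 80 down to 80 × 0.6 = 48, or 120 down to 120 × 0.6 = 72.

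**Step 5. Spread of time after dose.** The documents do not fix it. Table 4 sets no postdose time at Visit 7, so some spread exists even if every site doses in the same place. Mixing locations can widen it.

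**The case against.** The best defence is that 8.2.3 sends the reader to the SoA for what happens at each visit, and the SoA leaves Visit 7 blank in both in-clinic intake rows. Home dosing also fits the absence of a morning rule for Visit 7, Table 3, and the Table 4 request to combine the PK sample with other bloods. On this view the mention of Visit 7 in 8.2.3 is a slip. Blacked-out text in 6.1 and 6.5, or the Table 4 note on Visit 7 that cannot be read, may give the real instruction.

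Part of this stands. Home dosing is a coherent intention, and the hidden text is unknown. But the SoA does not resolve the matter, because its own footnote i still asks for predose samples at Visit 7. Section 6.5 contradicts itself in legible sentences. No hidden note can make 8.2.3 agree with Table 3.

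A reader might look to the amendment history to settle the location. It does not. The INT-4 entry puts other antiepileptic drugs in the clinic on the day of Visit 7 and does not mention study drug. The INT-1 entry had both taken at home. Both entries describe changes made at those amendments, and the conflict in the current text does not depend on them.

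**Conclusion.** The contradiction is real, rests on current legible text, and is minor. Its effect is a possible mix of predose and postdose Visit 7 laboratory samples, the same for any biomarker analysis, and a wider spread of time after dose in the descriptive Week 12 PK summary. Whether sites did differ is not known from the documents. The primary seizure endpoint is unaffected.

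Three stronger readings are tempting and not supported:

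- *In-clinic dose times would be lost.* Table 3 has a during-visit line for Visit 7, with its cells marked not applicable. Section 8.5 requires the actual time of the last dose before each PK sample, whether taken at home or in the clinic. Population PK is therefore largely protected.
- *The two readings differ by at least 2 to 3 hours after dose.* That figure takes 4 h for a home dose and 1 to 2 h for a clinic dose (4 − 2 = 2, 4 − 1 = 3). Table 4 sets no clinic time at Visit 7, and the general visit fast applies only when possible, so the figure is not a lower bound.
- *A planned Week 12 biomarker comparison is compromised.* SAP 5.7.3 calls the biomarker assessment potential and leaves its details to a separate document.

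**What to change.** Choose one location and align Sections 1.1, 6.1, 6.4, 6.5 and 8.2.3, the SoA and Tables 3 and 4.

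**Preferred: in the clinic, after the fasting draw.** This satisfies footnote i, 8.7 and 8.2.3 together.

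- Add Visit 7 to the in-clinic lists in 1.1 and 6.1, both SoA intake rows, and the morning rule (8.2.3 and footnote e).
- Correct the list in 6.4 to Visits 2, 4, 6 and 7, and delete the home-dose sentences in 6.4 and 6.5.
- In Table 3, have the participant record the day-before dose and the investigator the in-visit dose, for study drug and levetiracetam/brivaracetam.
- In Table 4, give the Visit 7 PK sample a stated postdose time (for example 1 h as at Visit 4, or 2 h as at Visit 2), drawn separately from the predose bloods.
- Limit the Visit 7 study-drug dose to participants still on treatment. Visit 7 is also the early-withdrawal visit, and Section 7.3 requires withdrawn participants to stop study drug, so those who have stopped must be explicitly exempt.

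**Alternative: at home.** Remove Visit 7 from the clinic lists in 8.2.3 and 6.5, and exempt it from footnote i and, where needed, from the 8.7 fast.

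Either way the cost is a protocol clarification and a site letter, with no extra visits or blood samples. The in-clinic option also needs a morning visit and a short wait for the postdose draw. For Visit 7 samples already taken, the dose times required by 8.5 can be used to label them predose or postdose.
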